11 LIST OF TABLES AND TABLE SHELLS

A list of tables and table shells will be prepared separately.

Appendix-1: List of ICD-10 Codes

Variable Used in Study	ICD-10 Code*	Additional rules on Data Extraction
Atrial fibrillation	I48	
Post-operative atrial fibrillation	8847772	Standard disease code
Valvular atrial fibrillation	8846941	Standard disease code
Rheumatic atrial fibrillation	I05	
	I06	
	I07	
	I08	
	I09	
Mechanical-valvular atrial fibrillation	T820	
Hyperthyroidism or thyrotoxicosis	E05	
Heart failure	I110	
	I500	
	I501	Exclude cardiac asthma
	I509	
Hypertension	H350	Include only hypertensive retinopathy and hypertensive neuroretinopathy
	I10	
	I110	
	I119	
	I120	
	I129	Include only hypertensive renal disease, hypertensive nephropathy and hypertensive nephrosclerosis
	I150	
Diabetes	E10	
	E11	
	E12	
	E13	
	E14	
Hemorrhage stroke	I60	
	I61	
	I62	Exclude non-traumatic extradural haemorrhage
Ischemic stroke	I63	
	3489032	standard disease code

	4371003	
	4379014	
	3448002	
	3448028	
	3489029	
	3489035	
	4379006	
TIA	H340	
	G450	
	G451	
	G458	
	G459	
Systemic embolism	I740	Include only abdominal aortic embolism
	I741	Include only aortic embolism
	I742	Include only acute arterial occlusive disease of arteries of upper extremities
	I743	Include only femoral arterial occlusion and acute arterial occlusive disease of arteries of lower extremities
	I744	
	I745	Include only iliac artery embolism
	I748	Include only hepatic artery embolism
	I749	Include only thromboembolism, embolic infarction, aortic embolism
Peripheral vascular disorder	I702	Include only atherosclerosis and arteriosclerosis obliterans
	I709	
	I731	Include only Buerger's disease
	I739	Exclude peripheral circulatory failure, cerebrovascular spasm, and angospasm pf the extremities
	I742	
	I743	
	I745	
	I748	Include only subclavian artery stenosis
Aortic plaque	4400011	Standard disease code
	8837393	Standard disease code
Coronary artery disease	I200	
	I201	
	I208	
	I209	

	I210	
	I211	
	I212	
	I213	
	I214	
	I240	
	I241	
	I248	
	I251	
	I252	Exclude calcification of coronary artery
	I255	
	I258	Exclude coronary arteritis
	I259	
Myocardial infarction	I200	Exclude intermediate angina syndrome, preinfarction syndrome, initial arbeits angina, intermediate coronary syndrome
	I210	
	I211	
	I212	
	I214	
	I240	
	I241	Exclude Dressler syndrome
Renal dysfunction	I120	
	I129	
	I139	
	N003	
	N009	
	N032	
	N033	
	N039	
	N040	
	N044	
	N049	
	N052	
	N055	
	N058	
	N059	
	N170	
	N171	
	N172	

	N178	
	N179	
	N189	
	N19	Exclude renal anemia, afunctional kidney, and alimentary proteinuria
Liver dysfunction	B150	
	B159	
	B162	
	B169	
	B171	
	B172	
	B178	
	B181	
	B182	
	B189	
	B199	
	K700	
	K701	
	K703	
	K709	
	K716	
	K720	
	K721	
	K729	
	K730	
	K732	
	K738	
	K739	
	K740	
	K741	
	K743	
	K744	
	K745	
	K746	
	K750	
	K751	
	K754	
	K759	
	K760	
	K761	
	K762	

	K763	
	K766	
	K767	
	K768	
	K769	
Cancer	C00	
	C01	
	C02	
	C03	
	C04	
	C05	
	C06	
	C07	
	C08	
	C09	
	C10	
	C11	
	C12	
	C13	
	C14	
	C15	
	C16	
	C17	
	C18	
	C19	
	C20	
	C21	
	C22	
	C23	
	C24	
	C25	
	C26	
	C30	
	C31	
	C32	
	C33	
	C34	
	C37	
	C38	
	C40	

	C41	
	C43	
	C44	
	C45	
	C46	
	C47	
	C48	
	C49	
	C50	
	C51	
	C52	
	C53	
	C54	
	C55	
	C56	
	C57	
	C58	
	C60	
	C61	
	C62	
	C63	
	C64	
	C65	
	C66	
	C67	
	C68	
	C69	
	C70	
	C71	
	C72	
	C73	
	C74	
	C75	
	C76	
	C78	
	C79	
	C80	
	C81	
	C82	
	C83	

	C84	
	C85	
	C88	
	C90	
	C91	
	C92	
	C93	
	C94	
	C95	
	C96	
	C97	
	D00	
	D01	
	D02	
	D03	
	D04	
	D05	
	D06	
	D07	
	D09	
	D10	
	D11	
	D12	
	D13	
	D14	
	D15	
	D16	
	D17	
	D18	
	D19	
	D20	
	D21	
	D22	
	D23	
	D24	
	D25	
	D27	
	D28	
	D29	
	D30	

	D31	
	D32	
	D33	
	D34	
	D35	
	D36	
	D37	
	D38	
	D39	
	D40	
	D41	
	D42	
	D43	
	D44	
	D45	
	D46	
	D48	

ICD-10, International Statistical Classification of Diseases and Related Health Problems

*: 7-digit numbers not beginning with alphabets are the standard disease code instead of ICD-10 code.

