7.3. Variables

Demographic and clinical characteristics are collected during the baseline period or at the index date.

Table 1: Demographic and clinical information of patients

<Eliquis>

<B0661120> Safety and effectiveness evaluation of patients with non-valvular atrial fibrillation treated with OACs: Comparison between NOACs and warfarin (CER3)

<Final ver.1.1><20180508>

Variable	Obtained from	Operational definition
Sex Category	Index date	Dichotomous variable equals 1 if sex is male and 2 if female
Age	Index date	Age (in years) at the index date
Physician specialty	Index date	Dichotomous variable equals 1 if a physician specialty on the index date is categorized into a cardiac specialty and 0 if others. Following specialties will be categorized as the cardiac specialty: cardiology stroke, cardiovascular surgery, pediatric cardiology, neurosurgery, cardiovascular medicine, and neurology. If there are ≥1 specialties but including the cardiac specialty, the physician specialty will be regarded as the cardiac specialty.
Hospital size (<500 beds or not)	Index date	Dichotomous variable equals 1 if hospital size on the index date is <500 beds and 0 if ≥500 beds.
Hospitalization status on index date	Index date	Dichotomous variable equals 1 if hospitalization status is inpatient and 0 if outpatient.
CHADS ₂	Baseline period	CHADS ₂ score will be calculated based on age and the presence of congestive heart failure, hypertension, diabetes, and stroke or TIA.
CHA ₂ DS ₂ -VASC	Baseline period	Score calculated by appointing 1 point each for congestive heart failure/left ventricle dysfunction, hypertension, diabetes, vascular disease (prior MI, peripheral arterial disease, or aortic plaque), age between 65-74, female gender; and 2 points each for age >75 years and prior stroke, TIA, or thromboembolism.
PT-INR (Prothrombin time-international normalized ratio)	Baseline period	Continuous variable. * Only available for patients treated with warfarin
Heart failure diagnosis in baseline	Baseline period	Dichotomous variable equals 1 if there are ≥1 diagnoses for heart failure ICD-10 or disease codes during the baseline period.
Coronary heart disease diagnosis in baseline	Baseline period	Dichotomous variable equals 1 if there are ≥1 diagnoses for coronary heart disease ICD-10 or disease codes during the baseline period.

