8.4 COVARIATES

We will use demographic and clinical information available at the index date and baseline period of the initiation prescription for apixaban, edoxaban, and warfarin cohorts.

Variable	Role	Operational definition
Sex Category	Baseline characteristic	Dichotomous variable equals 1 if sex is male and 2 if female
Age	Baseline characteristic	Age (in years) at the index date
Physician specialty	Baseline characteristic	Dichotomous variable equals 1 if a physician specialty on the index date is categorized into a cardiac specialty and 0 if others. Following specialties will be categorized as the cardiac specialty: cardiology stroke, cardiovascular surgery, pediatric cardiology, neurosurgery, cardiovascular medicine, and neurology. If there are ≥ 1 specialties but including the cardiac specialty, the physician specialty will be regarded as the cardiac specialty.
Hospital size (<500 beds or not)	Baseline characteristic	Dichotomous variable equals 1 if hospital size on the index date is <500 beds and 0 if ≥ 500 beds.
Hospitalization status on index date	Baseline characteristic	Dichotomous variable equals 1 if hospitalization status is inpatient and 0 if outpatient.
CHADS ₂	Baseline characteristic	CHADS ₂ score will be calculated based on age and the presence of congestive heart failure, hypertension, diabetes, and stroke or TIA.

CHA ₂ DS ₂ -VASC	Baseline characteristic	CHA ₂ DS ₂ -VASC score will be calculated based on age and the presence of congestive heart failure, hypertension, diabetes, stroke or TIA, vascular disease and sex category.
PT-INR (Prothrombin time-international normalized ratio)	Baseline period	Continuous variable. * Only available for patients treated with warfarin
Heart failure diagnosis in baseline	Baseline characteristic	Dichotomous variable equals 1 if there are ≥ 1 diagnoses for heart failure ICD-10 or disease codes during the baseline period.
Coronary heart disease diagnosis in baseline	Baseline characteristic	Dichotomous variable equals 1 if there are ≥ 1 diagnoses for coronary heart disease ICD-10 or disease codes during the baseline period.
Peripheral arterial disorder diagnosis in baseline	Baseline characteristic	Dichotomous variable equals 1 if there are ≥ 1 diagnoses for peripheral arterial disorder ICD-10 or disease codes during the baseline period.

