Myocardial infarction diagnosis in baseline	Baseline characteristic	Dichotomous variable equals 1 if there are ≥ 1 diagnoses for myocardial infarction ICD-10 or disease codes during the baseline period.
Hyperthyroidism or thyrotoxicosis in baseline	Baseline characteristic	Dichotomous variable equals 1 if there are ≥ 1 diagnoses for hyperthyroidism ICD-10 or disease codes during the baseline period.
Stroke, TIA or SE diagnosis in baseline	Baseline characteristic	Dichotomous variable equals 1 if there are ≥ 1 diagnoses for Stroke, TIA or systemic embolism ICD-10 or disease codes during the baseline period.
Renal dysfunction diagnosis in baseline	Baseline characteristic	Dichotomous variable equals 1 if there are ≥ 1 diagnoses for renal dysfunction ICD-10 or disease codes during the baseline period.
Liver dysfunction diagnosis in baseline	Baseline characteristic	Dichotomous variable equals 1 if there are ≥ 1 diagnoses for liver dysfunction ICD-10 or disease codes during the baseline period.
Bleeding diagnosis in baseline	Baseline characteristic	Dichotomous variable equals 1 if there are ≥ 1 diagnoses for bleeding ICD-10 or disease codes during the baseline period.
Hypertension diagnosis in baseline	Baseline characteristic	Dichotomous variable equals 1 if there are ≥ 1 diagnoses for hyper tension ICD-10 or disease codes during the baseline period.
Diabetes mellitus diagnosis in baseline	Baseline characteristic	Dichotomous variable equals 1 if there are ≥ 1 diagnoses for diabetes mellitus ICD-10 or disease codes during the baseline period.
Cancer diagnosis in baseline	Baseline period	Dichotomous variable equals 1 if there are ≥ 1 diagnoses for diabetes mellitus ICD-10 or disease codes during the baseline period.
Treated with antiplatelet drug in baseline	Baseline characteristic	Dichotomous variable equals 1 if there are ≥ 1 prescriptions of antiplatelet drug ATC or receipt codes during the baseline period.
Treated with NSAIDs in baseline	Baseline characteristic	Dichotomous variable equals 1 if there are ≥ 1 prescriptions of NSAIDs ATC or receipt codes during the baseline period.

Treated with gastric secretion inhibitor in baseline	Baseline characteristic	Dichotomous variable equals 1 if there are ≥ 1 prescriptions of gastric secretion inhibitor drug ATC or receipt codes during the baseline period.

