10 STATISTICAL METHODOLOGY AND STATISTICAL ANALYSES

10.1 STATISTICAL METHODS

10.1.1 Propensity Score Matching

In this study, matched cohorts (apixaban vs. warfarin, dabigatran versus warfarin, edoxaban vs. warfarin and rivaroxaban versus warfarin) will be created. Propensity scores will be estimated by unconditional logistic regression analyses that incorporate potential predictors of therapy as independent variables in the regression and cohort status as the outcome. The matching between warfarin group and each NOAC group (reference), 1:1 propensity score matching (PSM) method without replacement will be conducted. We will apply nearest neighbour method within caliper (width=0.2 times the standard deviation of the logit of the propensity score) matching technique. Standardized differences will be used to assess the balance of covariate between warfarin group and each NOAC group. If the standardized difference is less than 10%, the covariates are considered balanced. The following covariates will be included in the logistic regression:

- age on index date
- gender

- CHADS₂ score in baseline
- CHA₂DS₂-VASc score in baseline
- heart failure diagnosis in baseline
- coronary heart disease diagnosis in baseline
- peripheral arterial disorder diagnosis in baseline
- myocardial infarction diagnosis in baseline
- hyperthyroidism or thyrotoxicosis in baseline
- TIA diagnosis in baseline
- stroke or SE diagnosis in baseline
- renal dysfunction diagnosis in baseline
- liver dysfunction diagnosis in baseline
- bleeding diagnosis in baseline
- hypertension diagnosis in baseline
- diabetes mellitus diagnosis in baseline
- treated with antiplatelet drug in baseline
- treated with NSAIDs in baseline
- treated with gastric secretion inhibitor in baseline
- treated with statin-based drug in baseline
- treated with anti-hypertensives in baseline
- treated with anti-arrhythmics in baseline
- treated with beta-blockers in baseline
- treated with heparins in baseline
- cardioversion in baseline

The operational definitions for the above covariates are shown in the Section 6.4.

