14 APPENDIX-3: LIST OF ANY BLEEDING

Procedure for definition of “any bleeding”

Step 1. To extract the following group A or group B from MDV data base.

Group A: ICD-10 name includes [REDACTED] (bleeding)" or [REDACTED] (ecchymoma)"

Group B: Disease name includes [REDACTED] (bleeding)" or [REDACTED] (ecchymoma)"

Step 2. To select disease names considered to be relevant to side effect of OAC individually from disease names excluded in Step 1.

Step 3. To exclude disease names which are not considered to be relevant to side effect of OAC from the disease names included in Step 1.

ICD-10	ICD10Name
A162	Tuberculosis of lung, without mention of bacteriological or histological confirmation
A165	Tuberculous pleurisy, without mention of bacteriological or histological confirmation
B303	Acute epidemic haemorrhagic conjunctivitis (enteroviral)
D500	Iron deficiency anaemia secondary to blood loss (chronic)
D62	Acute posthaemorrhagic anaemia
D66	Hereditary factor VIII deficiency
D683	Haemorrhagic disorder due to circulating anticoagulants
D698	Other specified haemorrhagic conditions
D699	Haemorrhagic condition, unspecified
E078	Other specified disorders of thyroid
E274	Other and unspecified adrenocortical insufficiency
G361	Acute and subacute haemorrhagic leukoencephalitis [Hurst]
G951	Vascular myopathies
G968	Other specified disorders of central nervous system
H052	Exophthalmic conditions
H113	Conjunctival haemorrhage
H168	Other keratitis
H208	Other iridocyclitis
H210	Hyphaema
H313	Choroidal haemorrhage and rupture
H350	Background retinopathy and retinal vascular changes
H356	Retinal haemorrhage
H357	Separation of retinal layers
H405	Glaucoma secondary to other eye disorders
H431	Vitreous haemorrhage

ICD-10	ICD10Name
H448	Other disorders of globe
H470	Disorders of optic nerve, not elsewhere classified
H603	Other infective otitis externa
H669	Otitis media, unspecified
H738	Other specified disorders of tympanic membrane
H922	Otorrhagia
I213	Acute transmural myocardial infarction of unspecified site
I230	Haemopericardium as current complication following acute myocardial infarction
I312	Haemopericardium, not elsewhere classified
I600	Subarachnoid haemorrhage from carotid siphon and bifurcation
I601	Subarachnoid haemorrhage from middle cerebral artery
I602	Subarachnoid haemorrhage from anterior communicating artery
I603	Subarachnoid haemorrhage from posterior communicating artery
I604	Subarachnoid haemorrhage from basilar artery

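### The SAP's myocardial infarction code list omits I213, which the SAP itself titles an acute infarction, so the MI covariate, and probably the CHA2DS2-VASc vascular point, is understated for those patients

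*SAP*

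**What the plan says.** - SAP Appendix-1, myocardial infarction: I200, I210, I211, I212, I214, I240, I241. The only restrictions are name exclusions beside I200 ("Exclude intermediate angina syndrome, preinfarction syndrome, initial arbeits angina, intermediate coronary syndrome") and beside I241 (Dressler syndrome).
- SAP Appendix-1, coronary artery disease: 17 codes, among them I213 with no restriction and I252 with the note "Exclude calcification of coronary artery".
- SAP Appendix-3 (the any-bleeding list) prints the title of I213: "Acute transmural myocardial infarction of unspecified site".
- SAP 8.4 sets the MI flag to 1 on one or more "diagnoses for myocardial infarction ICD-10 or disease codes during the baseline period". SAP 10.1.1 lists "myocardial infarction diagnosis in baseline" among the propensity covariates, alongside coronary heart disease and CHA2DS2-VASc.
- Protocol 7.3, Table 1, gives one CHA2DS2-VASc point for "vascular disease (prior MI, peripheral arterial disease, or aortic plaque". SAP 8.4 builds the score from age and "congestive heart failure, hypertension, diabetes, stroke or TIA, vascular disease and sex category", and names no code list for the vascular part.

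**The concern.** The SAP classes as non-MI a diagnosis that it elsewhere titles an infarction. Run as written, the program would misstate the MI flag for these patients in the propensity model and in the baseline table. It would probably misstate CHA2DS2-VASc as well, which is another propensity covariate and a headline description of stroke risk.

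The planned diagnostics would not show the error. Balance is judged by standardized differences in the derived covariates, and if these are below 10% the Cox model carries index treatment alone (SAP 10.1.1 and 10.1.3). Balance on an incomplete flag looks the same as balance on a complete one.

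**Working it through.** The plan gives no figure to reproduce here. The check compares the printed lists.

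**1. Coronary list against MI list (Appendix-1).** All seven MI codes are in the coronary list, so the difference is 17 − 7 = 10 codes: I201, I208, I209, I213, I248, I251, I252, I255, I258, I259. Within the I21 block the coronary list has I210, I211, I212, I213 and I214. The MI list has the same run without I213.

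**2. What the documents call the omitted codes.** Appendix-3 titles I213 an acute transmural infarction. They print no title for I252; the only text beside it is the calcification note. I213 is thus an internal contradiction, while I252 can only be queried.

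**3. Which list feeds the vascular point.** Neither document says. Appendix-1 does hold a separate aortic plaque list (4400011, 8837393). Aortic plaque is not a covariate in SAP 8.4 or in the propensity list of SAP 10.1.1. In the readable text its only use is the vascular component in Protocol Table 1. That suggests Appendix-1 supplies the components of the score and that its MI list supplies prior MI. This is an inference, and some SAP text is blacked out.

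**4. A patient whose only vascular evidence is I213.** I213 is not in the peripheral vascular list (I702, I709, I731, I739, I742, I743, I745, I748) or the aortic plaque list.

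| Variable | As written | With I213 in the MI list |
|---|---|---|
| MI flag | 0 | 1 |
| Coronary heart disease flag | 1 | 1 |
| CHADS2 (no vascular item) | unchanged | unchanged |
| CHA2DS2-VASc, if the MI list feeds it | s | s + 1 |

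**5. Size for the descriptive data.** Let p be the share of patients whose only vascular evidence is an omitted infarction code. The mean score is then low by p × 1 point. The documents do not give p, so these shares are assumptions:

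- p = 1%: 0.01 × 1 = 0.01
- p = 5%: 0.05 × 1 = 0.05
- p = 10%: 0.10 × 1 = 0.10

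MI prevalence is understated by q, the share with an omitted infarction code and no listed MI code. Because q also counts patients who have a peripheral arterial or plaque code, q ≥ p.

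**6. Size for the propensity score.** In a main-effects logistic model the patient in step 4 keeps the coronary term but lacks the MI term and one unit of the score term. With fixed coefficients the linear predictor is off by b(MI) + b(score). Neither coefficient is known before fitting, so no hazard-ratio effect can be derived.

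**The case against.** The best counter-argument is that nothing is lost to the adjustment. Every I213 or I252 patient still has the coronary flag set, and that flag is a propensity covariate. The lists also apply identically to all five cohorts. The information is misallocated between two correlated covariates, and a material change in the hazard ratios is not shown. This stands, and it limits the point to the MI flag, the score and the baseline table.

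It is also fair that the link from the MI list to the vascular point is nowhere written, so the loss of a point is conditional. A peripheral arterial or aortic plaque code would restore it.

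A reader might infer more than the documents support:

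- **That I252 is a proven omission.** Its title is not printed. Because the score counts prior MI, the code should be looked up.
- **That I200 brings angina into the MI flag.** Four names under I200 are already excluded, and the documents do not show which names remain.
- **That the renal covariate is miscoded.** The renal list has five N17 codes but only N189 from N18. Neither document says that renal dysfunction should cover other N18 codes, shows that the database holds any, or gives its ICD-10 version. The flag can also be set by N19 (with the rule "Exclude renal anemia, afunctional kidney, and alimentary proteinuria") and by the hypertensive and glomerular codes listed. The choice of N189 is a point to confirm, and no bias factor for the hazard ratio can be computed from it.

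**Conclusion.** The I213 omission is a real inconsistency within the SAP. It makes the MI flag wrong for any patient whose only infarction code is I213. CHA2DS2-VASc is one point too low for such a patient if the MI list feeds the vascular component and no peripheral arterial or plaque code is present. The mean-score shift of 0.01 to 0.10 rests wholly on assumed shares of 1% to 10%.

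The effect on hazard ratios is probably small, because the coronary covariate still identifies these patients. A general claim that the propensity covariates are miscoded, or that the treatment comparison is biased by a stated amount, is not supported. The correction is worth making because it is specific, almost free, and not detectable from the planned balance checks.

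**What to change.** 1. Add I213 to the myocardial infarction list in SAP Appendix-1, or record why it is left out.
2. Look up I252 in the database's code master, and add it to the MI list if it denotes past infarction.
3. In SAP 8.4, state that the Appendix-1 myocardial infarction, peripheral vascular disorder and aortic plaque lists define the vascular component of CHA2DS2-VASc, in line with Protocol Table 1.
4. Recompute the MI flag and CHA2DS2-VASc before fitting the propensity models, or refit the models if they have already been run.
5. While the code master is open, confirm that taking only N189 from N18 is intended.

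The cost is a code-list edit, one sentence in the SAP and the re-derivation of two variables. No new data are needed.

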13 APPENDIX-2: LIST OF PROCEDURES CODES

Procedure	Procedure Code
Cardiac surgery	150138210
	150138310
	150138410
	150138510
	150359210
	150138710
	150140510
	150140610
	150140710
	150139010
	150140810
	150318010
	150317810
	150318110
	150331450
	150331550
	150331950
	150332050
	150317910
	150318210
	150140010
	150139210
	150153910
	150374910
	150375010
	150375110
	150260350
	150284310
	150359310
	150263310
	150375210
	150375310
	150375410
	160107550
	150139810
	150139910
	150318310
	150145710

Procedure	Procedure Code
	150145810
	150145910
	150146010
	150318410
	150318510
	150302770
	150143010
	150143110
	150331650
	150332150
	150318710
	150319010
	150319310
	150318810
	150319110
	150319410
	150328750
	150328850
	150331750
	150331850
	150332250
	150332350
	150318910
	150319210
	150319510
	150318610
	150141010
	150279510
	150279610
	150141410
	150141610
	150369950
	150141710
	150359470
	150143610
	150260050
	150143710
	150143810
	150141510

Procedure	Procedure Code
	150375570
	150375670
	150375770
	150319610
	150292910
	150139310
	150140910
	150242550
	150244910
	150245010
	150359510
	150359610
	150381150
	150381250
	150381350
	150381450
	150150010
	150381550
	150275910
	150359710
	150359810
	150359910
	150381650
	150381750
	150381850
	150381950
	150150110
	150382050
	150245110
	150245210
	150375870
	150375970
	150376070
	150141210
	150301310
	150267850
	150319710
	150151810
	150376110

Procedure	Procedure Code
	150139110
	150319810
	150138810
	150151910
	150320010
	150346410
	150320110
	150147150
	150144110
	150320210
	150320310
	150142710
	150139410
	150320410
	150142910
	150320510
	150260150
	150346510
	150145110
	150145010
	150376210
	150376310
	150143250
	150143350
	150143450
	150143550
	150283250
	150283350
	150283450
	150283550
	150144910
	150139610
	150142410
	150141810
	150141910
	150320610
	150142050
	150142110
	150142210

Procedure	Procedure Code
	150142310
	150142810
	150144010
	150320710
	150144210
	150144550
	150147410
	150147510
	150320810
	150320910
	150144410
	150144650
	150144750
	150146510
	150146610
	150321010
	150321110
	150321210
	150376470
	150146910
	150146810
	150321310
	150142510
	150329810
	150145310
	150329910
	150139510
	150330010
	150147010
	150330110
	150376570
	150321410
	150321510
	150376670
	150147310
	150145650
	150141310
	150321810
	150321610

Procedure	Procedure Code
	150321910
	150146710
	150321710
	150330210
	150330310
	150376770
	150293010
	150330410
	150145510
	150302870
	150145410
	150322010
	150322110
	150144310
	150147250
	150346610
	150144810
	150253810
	150253910
	150275610
	150346710
	150262810
	150303310
	150267310
	150140110
	150140210
	150140410
	150346910
	150347010
	150303210
	150322210
	150275210
	150275310
	150336910
	150337010
	150360010
	150148010
	150148110
	150147610

Procedure	Procedure Code
	150147910
	150147770
	150147870
	150347170
	150275870
	150262910
	150275710
	150266110
	150382650
	150266210
	150382750
	150301810
	150382850
	150303410
	150303510
	150360110
	150360210
	150360310
	150360410
	150303610
	150303710
	150322410
	150322610
Ablation	150346710
	150262810
	150303310
	150346870
	150370050
Electrical defibrillation	140051410
	140010310
	140055010
	150275210
	150275310
	150336910
	150337010
	150370550
Heart valve prosthesis implantation surgery	150141410
	150141610
	150141710

Procedure	Procedure Code
	150359470
	150369950
	150331950
	150332050
	150332150
	150328850
	150332250
	150332350
	150141510
	150375570
	150375670
	150375770
	150244910
	150359510
	150381150
	150381250
	150359710
	150359810
	150381650
	150381750
	150283450

